7.2 Determination of Response

All subjects will be evaluated for response. The Evaluation Team will be composed of the Investigators, and one outside physician. All of the clinical tests will be evaluated independently by each member of the Team for changes against the baseline findings. This evaluation will take place prior to each implantation or when the subject leaves the study. The individual subject's baseline established prior to the first implantation will be used for the entire study. A table will be constructed using the changes from baseline.

Outline of Response Rate				
TESTS	Baseline Prior to First Implantation	Results Prior to Second Implantation	Results Prior to Third Implantation	Results Prior to Fourth Implantation
Clinical Findings				
Symptoms				
Global Clinical Assessment				
Quality of Life				
Clinical Laboratory Tests (Abnormalities)				
Tumor Markers (Decrease)				
Imaging Studies (Evidence of Change, e.g., volume or area)				
CT				
PET				
MRI				
Rating Scale				
Major Improvement: 3				
Improvement: 2				
No Change: 1				

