3.2 Objectives for the advanced pancreatic cancer

3.2.1 Primary Objective

To determine the Response Rate (RR), at 2 weeks, 4 weeks, 8 weeks, 3 months, 6 months, 9 months, 12 months or longer as possible, of subjects treated with macrobeads after they have failed standard chemotherapeutic regimens or have decided not to pursue standard or experimental chemotherapy for treatment-resistant, metastatic pancreatic adenocarcinoma, where RR is defined as:

- Evidence of change in primary or secondary tumor size (volume, area) as well as state (necrosis, vascularization, metabolic rate) on PET-CT, as well as MRI and/or CT as appropriate
- Decrease in tumor markers (including CEA and CA 19-9) and specific biochemical parameter levels in plasma/serum
- Stable or improved quality of life as measured by EORTC QLQ-C30, weight, and pain control
- Stable or improved global clinical rating of subject by physician and/or nurse
- Increase in LDH consistent with tumor necrosis (significance of LDH changes will be determined in relation to imaging changes indicative of necrosis)

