4.6 Assessments

The objective of the proposed Phase II study of the RENCA macrobeads is, as stated above, to determine the human clinical efficacy of the cancer macrobeads in advanced pancreatic and colorectal cancer. Responses will be

assessed according to the usual categories of complete or partial response (with specification of percentage), and none/progression (with specification of percentage). Response assessment will be measured in terms of changes in volume of primary tumor and number of metastases as assessed by CT or MRI; tumor marker PSA, as well as the physician global clinical assessment; performance rating scale (Karnofsky or similar); quality of subject life as measured by the EORTC Quality of Life Scale. Alkaline phosphatase and lactic dehydrogenase will also be followed.

Other laboratory determinations to monitor subject response to the implantation of the macrobeads will include detection of inflammatory responses (CBC with differential WBC and platelet count, erythrocyte sedimentation rate, C-reactive protein, amylase, immunological changes, and cytokine production), RT-PCR (polymerase chain reaction) specific to e-MuLV DNA, plasma viremia, and antibodies to normal murine antigens.

A critical and unique addition to the endpoints for assessing efficacy will be, where possible, a careful search for and identification of the niches of cancer stem and other cells within the niche bodies of the tumors the macrobeads are being used to treat. Markers of the niche bodies used to identify them and study their state (numbers, integrity of surround blood vessels, degree of stress) will include HLA, CD44+, CD133+, p27, Ki67, and the Tunel assay for apoptosis. Determination of the presence or absence of circulating tumor cells will also be made. When possible/available, pathology specimens will be examined for cancer stem cell niches.

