5.7 Appropriateness of Measurements and Assessments

In the evaluation of a therapeutic entity for the treatment of a malignant condition such as advanced pancreatic or colon cancer, the following measurements are appropriate. The response of each subject to the intraperitoneal implantation of RENCA agarose-agarose macrobeads will be measured with respect to:

- primary tumor size
- response: complete, partial, stable disease, progression
- progression as defined in Section 3 of the protocol
- size or number of secondary/metastatic tumors; tumor markers or relevant biochemical parameters such as liver enzymes
- tumor metabolic activity as measured by ¹⁹F-fluorodeoxyglucose uptake (if applicable)
- cellular or humoral immune status
- cytokines
- inflammatory response
- global clinical assessment
- activities of daily living (ADL) rating/performance status
- symptom rating/ severity (including use of pain medications)

- quality of life
- neuropsychological status/cognitive function
- pain rating scale, if appropriate

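### The Section 7.2 response rating has no level for worsening and no column for the study-exit evaluation, so a subject who deteriorates is coded as stable or not coded in that rating

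*Protocol*

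**What the plan says.** Section 7.2 of the protocol sets the scope widely: "All subjects will be evaluated for response". The Evaluation Team, made up of the investigators and one outside physician, compares the clinical tests with the baseline taken before the first implantation. On timing: "This evaluation will take place prior to each implantation or when the subject leaves the study". On output: "A table will be constructed using the changes from baseline".

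The table that follows is titled as an outline of the response rate. Its columns are the baseline and the results before the second, third and fourth implantations. Its rows cover symptoms, global assessment, quality of life, laboratory tests, tumor markers and imaging. Under it stands a rating scale with three levels: "Major Improvement: 3", "Improvement: 2", and no change, coded 1.

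Two other sections give response categories. Section 4.6 lists "complete or partial response (with specification of percentage), and none/progression (with specification of percentage". Section 5.7 lists "response: complete, partial, stable disease, progression".

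In Amendment 11 the pancreatic primary objective (Section 3.2.1) is "To determine the Response Rate (RR), at 2 weeks, 4 weeks, 8 weeks, 3 months, 6 months, 9 months, 12 months or longer", followed by its own list of components.

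**The concern.** A rating of change in advanced cancer should be able to record deterioration, which is the expected course for many of these subjects: the Background section says that most patients with advanced pancreatic cancer die within a year. The lowest code on this scale means no change, and Section 7.2 gives no rule for a subject who is worse than baseline. The exit evaluation is where deterioration would most often be recorded, and it has no place in the table.

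Response Rate is the pancreatic primary objective in Amendment 11, and 7.2 is the section titled for determining response. Section 7.1 says that the pancreatic data will be used to plan a controlled Phase IIb protocol. A response summary taken from this rating would show improvement but could not show its opposite.

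**Working it through.** The plan states no figure for this rating, so there is none to reproduce. The check is a comparison of texts.

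**1. Levels available.**

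| Place | Better | Unchanged | Worse |
|---|---|---|---|
| Section 4.6 | complete, partial | none | progression, paired with none |
| Section 5.7 | complete, partial | stable disease | progression |
| Section 7.2 scale | 3 and 2 | 1 | no level printed |

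Section 5.7 separates stable disease from progression. Section 4.6 names progression but joins it to no response with a slash. The 7.2 scale does not name it at all.

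**2. What happens to a subject who is worse than baseline.** All subjects are to be rated and the codes are 3, 2 and 1. The rater can enter 1, which is the code for an unchanged subject, or enter nothing. The text does not say which.

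**3. Timing against columns.** The text requires a rating before each implantation or at study exit. The columns after baseline are three: before the second, third and fourth implantations. Implantations are at least three months apart, so the last column falls at about 3 × 3 = 9 months at the earliest. Two occasions have no column:

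- exit from the study at any point;
- the final formal visit, Day 120 after the fourth implantation (Section 5.1.25), at which imaging, markers and quality of life are collected.

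**4. Fit with the pancreatic objective.** Section 3.2.1 names seven times: 2, 4 and 8 weeks, and 3, 6, 9 and 12 months. The 7.2 columns correspond at best to three of them (3, 6 and 9 months). The rating is therefore an incomplete vehicle for that objective even apart from the missing level.

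**5. Where worsening is recorded.** Sections 3.2.2 and 5.8 define progression, including death. SAP Section 10.1.1 analyses time to death. SAP Sections 10.1.2 and 10.1.4 summarise changes from baseline in imaging and rating scales, and these can go in either direction. The SAP's lists of listings, tables and figures (Sections 16.1 to 16.3) contain nothing based on the 1-to-3 rating.

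**6. Who is affected.** The scale applies to both cohorts, but response is primary only for pancreatic cancer: 40 of the 74 planned subjects (Protocol Appendix 3, item 9).

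**The case against.** The strongest objection is that the rating feeds no planned analysis. Appendix 3 of the protocol sends the primary and secondary analyses to the SAP. The SAP says that it supersedes the protocol's statistical considerations and that response rate was modified, and it never mentions this scale. This stands, and it is the main reason for the low severity. It does not remove the point. The SAP was written for Amendment 10. Amendment 11 attributes only the colorectal objectives to the SAP (Section 3.1) and keeps Response Rate as the pancreatic primary objective. The SAP's only response definition is a tumor-marker one (Section 10.1.3).

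A second objection is that a final row may have been lost when the table was read from PDF. This cannot be excluded. The scale is the last item before Section 8, and other tables were read imperfectly: several laboratory rows of the Appendix 2 schedule show only the screening mark, although the visit text repeats those tests throughout. The signed document has to be checked first.

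A third is that the table is only an outline and the text already mandates the exit evaluation. That is fair for the missing column taken alone. It does not supply a code to enter at that evaluation.

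A reader might be tempted by three stronger readings, none of which the documents support:

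- **That mean ratings would be biased upward by a calculable amount.** Neither document says that the codes are averaged, or combined across tests or raters. Any such figure would describe a statistic that is not planned.
- **That the trial cannot tell progressing subjects from stable ones.** It can, through the progression definitions, mortality and signed changes. Only this rating cannot. Within the same table the imaging row is neutral as to direction, although the marker row mentions only a decrease.
- **That subjects who worsen would drop out of the analysis.** Section 7 says that data from all subjects, including withdrawals, will be analysed, and Appendix 3 keeps all implanted subjects in the efficacy population. A missing code is not an exclusion.

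**Conclusion.** The point holds in a limited form. As printed, the 7.2 rating cannot record worsening, and its table has no cell for an evaluation that the text requires. This conflicts with the progression category in Sections 4.6 and 5.7. The consequence is confined to the response rating that Amendment 11 offers for the pancreatic Response Rate objective. It does not touch the mortality analysis or the SAP's summaries of change.

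Severity is low. No numerical size can be attached, because the plan does not say how the codes would be summarised. The conclusion assumes that the printed scale is complete. If the signed protocol has a worsening row, only the missing columns remain, and they are a minor matter of layout.

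**What to change.** First check the Section 7.2 table in the signed protocol for a lost row. If there is none:

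- add at least one worsening or progression level to the scale, with a sentence on how deaths and withdrawals are coded;
- add a column for study exit and one for the final Day 120 visit;
- report the percentages improved, unchanged and worse, with all implanted subjects of the cohort in the denominator;
- align the levels with Sections 4.6 and 5.7, and state whether no response and progression are reported separately.

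How many worsening levels to use is a matter of choice; one is enough to remove the defect. If the rating will not be analysed, delete the scale and say so, and state in 7.2 what determines the pancreatic response instead.

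The cost is protocol wording and a small change to the rating form. No new assessments are needed, because the exit evaluation and the Day 120 visit are already required.

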8 STUDY MANAGEMENT

8.1 Recruitment and Consent Procedures

Subjects will be recruited by physician referral. Full informed consent will be obtained prior to admission by one of the physician investigators. The hospital and state guidelines for obtaining consent prior to HIV testing will be followed.

8.2 Regulatory Guidelines

The study will be performed in accordance with United States IND regulations (21 CFR Part 312), the guidelines of the International Conference on Harmonization (ICH), Good Clinical Practice (GCP) Guidelines, and the most recent guidelines of the Declaration of Helsinki. These Guidelines will be on file in the Investigator's office and in The Rogosin Institute Clinical Research Program Operating Procedure Manual and, in addition, are available on the FDA's Web Site.

8.3 Institutional Review Board

Conduct of the study must be approved by an appropriately constituted Institutional Review Board (IRB). Approval is required for the study protocol, protocol amendments, informed consent forms, subject information sheets, and advertising materials (if any). No study drug will be shipped to the study center until written IRB authorization has been received by the Investigator or his or her representative.

8.4 Informed Consent

For each subject enrolled into the study, written informed consent will be obtained prior to any protocol-related activities. As part of this procedure, the principal investigator or appropriate personnel must explain orally and in writing the nature, duration, and purpose of the study, and the action of the study drug in such a manner that the subject is aware of the potential risks, inconveniences, or adverse effects that may occur. Subjects should be informed that they could withdraw from the study at any time. If the subject decides to withdraw from the

study, he or she will be asked if they would agree to continue to be monitored. They will receive all information that is required by federal regulations and ICH guidelines. The Principal Investigator will have on file a copy of the IRB-approved Informed Consent form prior to the start of the study.

8.5 Data Monitoring and Safety Board

The Data Safety and Monitoring Board will be provided with detailed safety information from the trial. This information will include information on adverse events, clinical laboratory results, and the results of all imaging studies. They are responsible along with the Investigator and The Rogosin Institute's Medical Monitor for providing oversight and monitoring of the safety of the participants in the study.

8.6 Study Documentation

By signing a copy of Form FDA 1572, the Principal Investigator acknowledges that he or she has a copy of the Investigator's Brochure and has reviewed the latest version. In addition, he or she will comply with the protocol and the provisions stated in Form FDA 1572. No changes in this protocol can be made without the written approval of the IRB and the FDA, unless the change is to protect the immediate safety of a subject. If changes are made to protect the safety of a subject, approval of the IRB and the FDA will be obtained as soon as possible.

The investigator will have the following forms and documents on file:

- Original, signed Form FDA 1572
- Curricula vitae for all investigators listed on Form FDA 1572
- Copy of principal investigator's state medical license
- Signed protocol signature page
- List of IRB members and their occupations/affiliations or multiple assurance number
- Letter indicating IRB approval to conduct the protocol
- Copy of IRB-approved informed consent form
- Laboratory certification records and reference ranges
- A statement of financial disclosure

A Case Report Form will be used to collect the data from the ongoing clinical study. This Case Report Form will be compiled in relationship to the protocol. In addition, to the pages for the collection of the results of all evaluations,

there will be sections for the entry of text to describe the progress of the subject and any significant events.

8.7 Study Monitoring and Auditing

This study will be monitored as outlined in 21CFR§312.50 and 21CFR§312.56, the Guidelines of Good Clinical Practice (ICH-E6), and The Rogosin Institute Clinical Research Program Operating Procedures. Monitoring will include personal visits and telephone communication to assure that the investigation is conducted according to the protocol and Guidelines of Good Clinical Practice (ICH-E6). Review of Case Report Forms (CRF) at the study center will include a review of printed or electronic forms for completeness and clarity, and consistency with source documents available for each subject. Note that a variety of original documents, data, and records will be considered as source documents in this trial. The CRF itself is not to be used as a source document under any circumstances, although some of the original source documents, such as those reporting laboratory values/data will themselves be electronic. Physician and nursing records will also be only electronic and so will form original source documents. The electronic records will be recorded in MIQS, a clinical data collection system that is compliant with all FDA-mandated regulatory requirements.

8.8 HIPAA

This study will be conducted in compliance with the protocol, FDA regulations, ICH, and GCP guidelines, and all other applicable federal, state, and local laws, rules, regulations, ordinances and guidelines, all other relevant professional standards, all requirements of the host institution or facility, and the Statement of Investigation, FDA Form 1572, as described in 21CFR§312.53, which the investigator has completed and signed, in the performance and documentation of the study. Without in any way limiting the foregoing, the investigator shall obtain valid advance written informed consent and advance written authorization for use and disclosure of protected health information from each of the subjects participating in the study and shall retain such documentation after completion of the study.

Coagulation Panel ²	X																						
Erythrocyte sedimentation rate	X																						
Comprehensive Metabolic Panel ³	X																						
GGT ⁴	X																						
Amylase ⁵	X																						
Lipase ⁵	X																						
Lactate Dehydrogenase	X																						
C-Reactive Protein	X																						
Bilirubin, Direct	X																						
Hepatitis Panel ⁶	X																						
HIV	X																						
Serum Pregnancy (Qualitative) ⁷	X																						
Immunoglobulin Levels ⁸	X																						
Cytokine Panel ⁹	X																						
Cellular Immune Function ¹⁰	X																						
Ecotropic Murine Leukemia Virus	X																						

	Screening	Visit 1 / Day 0	Visit 2 / Day 14	Visit 3 / Day 30	Visit 4 / Day 60	Visit 5 / Day 90	Visit 6 / Implant 2	Visit 7 / Day 14	Visit 8 / Day 30	Visit 9 / Day 60	Visit 10 / Day 90	Visit 11 / Implant 3	Visit 12 / Day 14	Visit 13 / Day 30	Visit 14 / Day 60	Visit 15 / Day 90	Visit 16 / Implant 4	Visit 17 / Day 14	Visit 18 / Day 30	Visit 19 / Day 60	Visit 20 / Day 90	Visit 21 / Day 120	Follow-Up ¹²
Immunohistochemical & Gene Array Analysis (when indicated)		X					X					X					X						
Murine Allergen Skin Test with positive and negative controls	X					X					X												
Circulating Tumor Cells	X		X	X	X	X		X	X	X	X		X	X	X	X		X	X	X	X	X	
Macrobeads Implantation (8 per kg body wt)		X					X					X					X						
Cefazolin (Prophylaxis – 1 gm)		X					X				X						X						
Chest X-Ray (PA/lateral)	X					X					X						X						
CT Scan Chest (Non-Contrast) ¹¹	X					X					X						X						
MRI of Abdomen ¹¹	X					X					X						X						X
MRI of Pelvis ¹¹	X					X					X						X						X
Tumor Mass Biopsy (where indicated)		X					X										X						X
PET-CT Scan Whole Body	X					X					X						X						X ¹¹
Radionuclide Bone Scan ¹¹																							

¹ Hematology Profile: WBC, RBC, hemoglobin, hematocrit, MCV, MCH, MCHC, RDW, platelets, automated differential WBC

² Coagulation Panel: PT, PTT, INR

³ Comprehensive Metabolic Panel: CO₂, sodium, potassium, chloride, creatinine, BUN, calcium, total protein, albumin, total bilirubin, alkaline phosphatase, AST, ALT, glucose

⁴ GGT: gamma glutamyl-transpeptidase

⁵ Amylase and lipase are done at baseline, then as medically necessary for individual subjects

⁶ Hepatitis Panel: Hepatitis B, C and E

⁷ Serum pregnancy only for females of childbearing potential

⁸ Immunoglobulin Levels: IgA, IgG, IgE and IgM

The efficacy/safety population is defined as all evaluable subjects regardless of subject compliance with protocol procedures. This population will be used in the primary analysis for assessment of efficacy. Efficacy sub-analyses may be performed on various subsets of subjects, such as those with no major protocol deviations or those who continued in the study for the entire treatment period (i.e., did not withdraw prematurely). One of the sub-analyses will include efficacy response after one, two, three, and/or four implantations.

All evaluable subjects enrolled in the study who complete at least one implantation procedure will be included in the safety population and considered evaluable for toxicity and safety. The efficacy and safety populations do not differ. All treatment related toxicities will be recorded and then tabulated at the end of the study. All treatment related toxicities will be recorded and then tabulated at the end of the study.

Screen Failures

All subjects who sign an Informed Consent but for any reason are not implanted will be considered screen failures. These subjects will be listed and the reasons for not being implanted listed and described.

5. Descriptive analyses

Measured outcome variables will be summarized overall and by relevant demographic and baseline variables. Descriptive statistics such as frequencies and relative frequencies will be computed for all categorical variables. Numeric variables will be summarized using simple descriptive statistics such as the mean, standard deviation and range. A variety of graphical techniques will also be used to display data, for example, histograms, boxplots, scatterplots, etc.

6. Primary statistical analyses

The primary objectives are outlined in Section 3 of this protocol. The analysis will be performed as detailed in Statistical Analysis Plan (SAP).

7. Secondary statistical analyses

The secondary objectives are outlined in Section 3 of this protocol. The analysis will be performed as detailed in Statistical Analysis Plan (SAP).

8. Stopping rules

In order to protect subjects from excessive toxicities possibly associated with the study treatment the following stopping rule will be utilized: if 3 or more subjects experience a grade 5 adverse event deemed possibly related to treatment, accrual will be halted and a thorough investigation will take place before the re-opening of accrual may be considered. The probability of excising the stopping rule within this study is a function of the true unknown probability of a grade 5 adverse event possibly related to the treatment corresponding to the study population. The table below contains the probability of observing at least 3 such toxicities in the 30 subjects for a variety of values of the true probability within the population.

True probability of treatment related toxicity	5%	10%	20%	30%
Probability of stopping the study based on 30 subjects	19%	59%	96%	99.8%

The calculations above are based on the assumption that our study sample may be treated as a random sample from the population of interest. As can be seen there does exist acceptable properties associated with the stopping rule.

9. Sample size justification

Since the primary objectives are addressed through estimation and not formal hypothesis testing, the original sample size of 20 colorectal subjects and 10 pancreatic subjects was based on the expected precision corresponding to the estimates of the progression at appropriate intervals and toxicity rates. We believe that these statistical goals will be fulfilled with the current intended sample size of 74 patients, of which, 40 patients will be pancreatic cancer type. The precision associated with these estimates is a function of the true unknown parameter value and the sample size used in the calculation. Note that a true rate of 50% represents the worst case scenario with in regards to precision and therefore we may take precision at that point to be an upper bound of expected accuracy in the estimation of study parameters. Calculations reveal that the precision associated with estimates based on the colorectal subjects will be at most 22 percentage points. In the case of pancreatic subjects, the corresponding quantity is 31 percentage points.

10. References

Brookmeyer, R. and Crowley, J.J. (1982). A confidence interval for the median survival time. *Biometrics*; 38:29-41.

Clopper, C.J. and Pearson, E.S. (1934). The use of confidence or fiducial limits illustrated in the case of the binomial. *Biometrika*; 26:404-413.

